17.2.2. Analysis of secondary endpoints and secondary analyses

Safety and tolerability of pembrolizumab in combination with rituximab

As this is continuous treatment, care will be taken to assess the burden of adverse events over time rather than just the worst grades seen.

Rates of adverse events (as assessed by CTCAE version 5.0) will be presented in four ways:

1. Worst grade seen of each event, i.e. the number of patients who experience a grade 1-2 or 3+ event at any time point.
2. Worst grade seen of each event per cycle, i.e. the number of patients who experience a grade 1-2 or 3+ event during each cycle.
3. Proportion of cycles where patients experience a grade 1-2 or grade 3-4 AE. This may also be presented by the number of cycles depending on the numbers of patients stopping treatment.
4. Median number of grade 1-2 or 3+ AEs (of any type) experienced at each cycle.

Analyses 3-4 may focus on clinical events only i.e. excluding lower level biochemical and haematological events which may not have an impact on the patient's quality of life.

Depending on the frequency of adverse events, we may also look at duration of some events, possibly as a proportion of the time on treatment.

AEs of special interest will be reported in more detail, with events of any grade presented.

All adverse event analysis will be descriptive.

Best response and time to best response.

The best response is the best response seen from the start of treatment; all response time points will be included.

Time to maximal response to treatment will be calculated as the time from the date of registration until the date of the best response. This will be presented as the median and range and will be reported for responding patients only.

Time to next treatment

Time to next treatment will be analysed using Kaplan-Meier survival analyses, with the time calculated from the date of registration to the date of the start of the next line of therapy. Patients who do not start a further line of treatment will be censored at the date last seen/date of death. The median (if applicable) and rates at 1 and 2 years will be presented.

Progression free survival

Progression free survival will be analysed using Kaplan-Meier survival analyses, with the time calculated from the date of registration to the date of progression/death. Patients who are alive and progression free will be censored at the date last seen. The median (if applicable), rates at 1 and 2 years and a Kaplan-Meier curve will be presented.

Overall survival

Overall survival will be analysed using Kaplan-Meier survival analyses, with the time calculated from the date of registration to the date of death. Patients who are alive will be censored at the date last seen. The median (if applicable), rates at 1 and 2 years and a Kaplan-Meier curve will be presented.

Quality of life

Quality of life is assessed using the QLQ-30 questionnaire at baseline and at week 24. Differences between baseline and week 24 will be compared using paired t-tests and changes between baseline and week 24 may also be compared to historical data from the R2W trial.

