2.1.7. Scientific rationale for combining Pembrolizumab and Rituximab in WM

The manageable tolerability of anti-PD-1 mAb pathway blockers and their unique mechanism of action are encouraging but to increase the response rate and depth of response combination therapy approaches appear to be required. Given the proven efficacy, well understood toxicity and proven ability to combine with other agents

(including cytotoxic chemotherapy and targeted small molecules such as ibrutinib and idelalisib) rituximab is attractive partner for such immunotherapy combinations.

Rituximab has proven clinical efficacy in WM and is widely used in the relapsed/refractory setting. In general, there is evidence of enhanced efficacy of rituximab combination therapy compared with monotherapy alone (Santos-Lozano et al, 2016). There is some rationale to hypothesise that pembrolizumab and rituximab could have a synergistic effect. Antibody and complement dependent cell mediated cytotoxicity may generate neo-antigens and create an inflammatory milieu, which may further prime T-cell activation. Also, the apparent limited activity of pembrolizumab as a single agent would inform a combination as a more logical approach, especially in the presence of some recently presented data looking at this combination in relapsed follicular lymphoma (Nastoupil et al, 2017). 30 patients treated with the combination led to an overall response rate of 64% and a CR rate of 48%, with a manageable toxicity profile, with immune AEs generally being grade 1-2.

The aim of this trial is to investigate the safety and efficacy of rituximab in combination with pembrolizumab in patients with relapsed WM.

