8.4.2. Pembrolizumab related adverse events

Immune related adverse events

If a patient experiences a pembrolizumab immune-related event, trial treatment should be withheld or discontinued as per the table below.

Where treatment is withheld, treatment should resume once the adverse event has reduced to grade 1 or 0 (as per table below). Corticosteroid taper should be initiated upon the adverse event improving to grade 1 or less and continue to taper over at least 4 weeks. Tapering should be performed as per local clinical practice.

For severe and life-threatening immune related adverse events, IV corticosteroid should be initiated first followed by oral steroid. Other immunosuppressive treatment should be initiated if immune related adverse events cannot be controlled by corticosteroids.

Toxicity Management Guidelines for Immune-related AEs associated with Pembrolizumab

Immune-related AEs	Severity grade CTCAE v5.0	Action taken	irAE management	Monitor and follow-up
Pneumonitis	Grade 2	Withhold treatment	
 Administer corticosteroids (initial dose of 1-2 mg/kg prednisolone or equivalent) followed by taper Add prophylactic antibiotics for opportunistic infections 	
 Monitor participants for signs and symptoms of pneumonitis Evaluate participants with suspected pneumonitis with radiographic imaging and initiate corticosteroid treatment
	Grade 3 or 4, or recurrent Grade 2	Permanently discontinue treatment		
Diarrhoea / Colitis	Grade 2 or 3	Withhold treatment	
 Administer corticosteroids (initial dose of 1-2 mg/kg prednisolone or equivalent) followed by taper 	
 Monitor participants for signs and symptoms of enterocolitis (i.e., diarrhoea, abdominal pain, blood or mucus in stool with or without fever) and of bowel perforation (i.e., peritoneal signs and ileus). Participants with \geq Grade 2 diarrhoea suspecting colitis should consider GI referral and performing endoscopy to rule out colitis. Participants with diarrhoea/colitis should be advised to drink liberal quantities of clear fluids. If sufficient oral fluid intake is not feasible, fluid and electrolytes should be substituted via IV infusion.
	Grade 4 or recurrent Grade 3	Permanently discontinue treatment		

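### All four planned adverse event presentations pool grade 1 with grade 2, although the protocol withholds or stops both drugs at grade 2 in most immune-related event groups

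*Combined protocol and SAP*

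**What the plan says.** Section 17.2.2 lists four numbered presentations of adverse events:

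- Presentation 1, by event: "Worst grade seen of each event, i.e. the number of patients who experience a grade 1-2 or 3+ event at any time point".
- Presentation 2, the same by cycle: "the number of patients who experience a grade 1-2 or 3+ event during each cycle".
- Presentation 3, taking cycles as the unit: "Proportion of cycles where patients experience a grade 1-2 or grade 3-4 AE".
- Presentation 4, a count across event types: "Median number of grade 1-2 or 3+ AEs (of any type) experienced at each cycle".

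Presentations 3 and 4 may be limited to clinical events, with this exclusion: "excluding lower level biochemical and haematological events which may not have an impact". The impact meant is that on quality of life. A separate line adds: "AEs of special interest will be reported in more detail, with events of any grade presented". The duration of some events may also be examined. All of this analysis is descriptive.

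Section 8.4.2 sets the actions for immune-related events by CTCAE grade. On resumption it says: "Where treatment is withheld, treatment should resume once the adverse event has reduced to grade 1 or 0". Under 8.4.1 a delay applies to both drugs, and under 8.5 so does discontinuation.

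**The concern.** Tolerability is part of the trial's overall aim and, with safety, a secondary endpoint. With a single arm and no planned test, the tolerability conclusion rests on these descriptive tables. Section 17.2.2 sets out to describe the burden of events over time and not only the worst grades.

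For most immune-related events, the protocol's own rules separate grade 1 from grade 2. The planned tables remove that distinction. Take two patients with the same named event, one at grade 1 with no change to treatment and one at grade 2 with both drugs withheld. They are counted in the same band. A reader of the results could not tell how much of that band reached the protocol's usual threshold for a hold. Section 2.1.7 shows how such a band can be read: it describes an earlier lymphoma cohort's toxicity as manageable, "with immune AEs generally being grade 1-2".

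**Working it through.** The plan states no figure on this point to reproduce. The check is a count and a comparison of sections.

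**Step 1: grade bands in 17.2.2.** Presentations 1, 2 and 4 use 1-2 against 3+. Presentation 3 uses 1-2 against 3-4. Pooled: 4 of 4.

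**Step 2: action at grade 2 in the 8.4.2 table.**

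| Event group | Action at grade 2 | Hold or stop |
|---|---|---|
| Pneumonitis | Withhold; permanent stop if recurrent | Yes |
| Diarrhoea/colitis | Withhold | Yes |
| AST/ALT or bilirubin | Withhold | Yes |
| Type 1 diabetes/hyperglycaemia | No grade 2 rule | No |
| Hypophysitis | Withhold | Yes |
| Hyperthyroidism | Continue | No |
| Hypothyroidism | Continue | No |
| Nephritis | Withhold | Yes |
| Neurological | Withhold | Yes |
| Myocarditis | Permanent stop (withheld already at grade 1) | Yes |
| Exfoliative skin conditions | Rule depends on diagnosis, not grade | No |
| All other immune-related | Withhold if persistent | Yes |

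- Hold or stop at grade 2: 8/12 = 67%.
- Among groups that have a grade 2 rule: 8/10 = 80%.
- Without the catch-all row: 7/11 = 64%.
- Groups with any permanent stop at grade 2: 2/12 (myocarditis; recurrent pneumonitis). Section 8.5 adds a second grade 2 pembrolizumab infusion reaction despite premedication.

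These rules act at grade 2 in most groups on each count, and mainly by withholding.

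**Step 3: does anything else in the plan fill the gap?**

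- *Events of special interest.* These are reported at any grade, but 12.4 limits them to a pembrolizumab overdose above five times the dose and one combined liver laboratory pattern. Immune-related events as a class are not covered.
- *Duration analysis.* It is optional and does not split grades.
- *Action taken.* Section 17.2.2 plans no table of events that led to withholding, delay or discontinuation.
- *Biochemical events.* Section 8.3.1 delays a cycle on AST/ALT or bilirubin limits. Section 8.4.2 withholds for grade 2 liver-test events and for grade 2 nephritis with raised creatinine. The optional exclusion in analyses 3 and 4 does not define which events are lower level, so it does not guarantee that such events stay in.

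**Step 4: size.** The documents give no expected rate of grade 2 immune-related events, so the number of patients cannot be derived. For scale only, and as an assumption: 5% of 42 is 0.05 × 42 = 2.1 patients, and 30% is 0.30 × 42 = 12.6. The point depends on neither figure.

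**The case against.** The strongest case for the plan has four parts.

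*The tables hide less than the pooling suggests.* A reader might infer that grade 2 myocarditis shares a cell with a trivial grade 1 event of another kind. In presentations 1 and 2 it does not, because both are by event. Only presentation 4 expressly mixes types, and presentation 3 is unclear. Nor is treatment-limiting toxicity as a whole concealed, since events of grade 3 or above remain visible. This stands, and it narrows the point to grade 1 against grade 2 within a named event.

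*Grade 2 is not the threshold throughout the regimen.* Myocarditis is acted on at grade 1. Treatment continues at grade 2 for both thyroid groups. Other pembrolizumab-related events under 8.4.4 are withheld at grade 3 and stopped at grade 4, with listed exceptions, so the planned cut suits them. Rituximab events follow product information that is not in the documents. This also stands. Splitting the grades would not by itself identify treatment-limiting events, which is why counts by action taken are needed too.

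*The loss of biochemical events is only possible.* The exclusion is optional, and the events would remain in presentations 1 and 2. That is correct. The gap is that the plan does not rule the loss out.

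*The consequence is limited.* There is no tolerability threshold, safety oversight under 12.6 is not tied to these bands, and CTCAE grade is recorded, so finer tables could be made later. This limits the severity. It does not remove the case for fixing the tables before the results are seen.

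**Conclusion.** The point holds as a reporting weakness. All four numbered presentations pool grades 1 and 2, the 8.4.2 table withholds or stops both drugs at grade 2 or persistent grade 2 in 8 of 12 event groups, and no other planned output separates the two.

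Three stronger readings are tempting, and the documents do not support them:

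- *Grade 2 events generally end treatment.* Withholding is the usual action, and permanent stops at grade 2 are confined to the three situations in the working.
- *The plan calls these events low grade, or its tolerability conclusion is bound to look too favourable.* The plan labels the band only by its grades and sets no criterion for tolerability. The remark in 2.1.7 concerns a different cohort.
- *A known number of patients would be missed.* No event rate is given, so any number is an assumption.

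The conclusion rests on the text of 17.2.2, 8.4.1, 8.4.2, 8.5 and 12.4 alone. The primary endpoint and sample size are unaffected. It is a worthwhile, inexpensive improvement.

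**What to change.** In 17.2.2:

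- In presentations 1 to 3, show grade 1, grade 2 and grade 3+ separately for events managed under 8.4.2 and 8.4.3. The planned cut can stay for other events.
- Report the number of patients whose adverse event led to permanent discontinuation. Section 15.2 already requires the reasons for discontinuing to be recorded on the case report forms.
- Report the number whose adverse event led to treatment being withheld, where the treatment forms record the reason for a delay. The documents do not describe what those forms contain or show that they link a given event to a temporary hold, so this should be checked first.
- State that a biochemical event that led to a hold or stop is not dropped from analyses 3 and 4.

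The grade split needs no new data: 12.2 requires a CTCAE grade for every event, and the per-cycle split uses the same grades as the plan's own per-cycle bands. The cost is slightly longer tables. Nothing in the treatment rules changes.

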2.1.6. Clinical experience of pembrolizumab

Pembrolizumab is a potent and highly selective humanised monoclonal antibody (mAb) of the IgG4/kappa isotype designed to directly block the interaction between PD-1 and its ligands, PD-L1 and PD-L2. Available pharmacokinetic (PK) results in patients with melanoma, non-small cell lung cancer (NSCLC), and other solid tumour types support a lack of meaningful difference in PK exposures obtained at a given dose among tumour types. An open-label Phase 1 trial (PN001) in melanoma patients has been conducted to evaluate the safety and clinical activity of single agent pembrolizumab. The dose escalation portion of this trial evaluated three dose levels, 1 mg/kg, 3 mg/kg, and 10

mg/kg, administered every 2 weeks (Q2W) in patients with advanced solid tumours (Patnaik et al, 2015). All three dose levels were well tolerated and no dose-limiting toxicities were observed. This first in human study of pembrolizumab showed evidence of target engagement and objective evidence of tumour size reduction at all dose levels. No maximum tolerated dose (MTD) has been identified.

In KEYNOTE-001, two randomized cohort evaluations of melanoma patients receiving pembrolizumab at a dose of 2 mg/kg versus 10 mg/kg every 3 weeks (Q3W) have been completed [ref]. The clinical efficacy and safety data demonstrate a lack of clinically important differences in efficacy response or safety profile at these doses. For example, in Cohort B2, advanced melanoma patients who had received prior ipilimumab therapy were randomized to receive pembrolizumab at 2 mg/kg versus 10 mg/kg Q3W. The overall response rate (ORR) was 26% (21/81) in the 2 mg/kg group and 26% (25/79) in the 10 mg/kg group (full analysis set (FAS)). The proportion of patients with drug-related adverse events (AEs), grade 3-5 drug-related AEs, serious drug-related AEs, death or discontinuation due to an AE was comparable between groups or lower in the 10 mg/kg group.

Available pharmacokinetic results in patients with melanoma, NSCLC, and other solid tumour types support a lack of meaningful difference in pharmacokinetic exposures obtained at a given dose among tumour types. Population PK analysis has been performed and has confirmed the expectation that intrinsic factors do not affect exposure to pembrolizumab to a clinically meaningful extent. Taken together, these data support the use of lower doses (with similar exposure to 2 mg/kg Q3W) in all solid tumour indications.

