12. PHARMACOVIGILANCE

12.1. Definitions

The following definitions have been adapted from Directive 2001/20/EC, ICH E2A “Clinical Safety Data Management: Definitions and Standards for Expedited Reporting” and ICH GCP E6.

Adverse Event (AE)

Any untoward medical occurrence in a patient treated on a trial protocol, which does not necessarily have a causal relationship with an IMP. An AE can therefore be any unfavourable and unintended sign (including an abnormal laboratory finding), symptom or disease temporally associated with the use of an IMP, whether or not related to that IMP. See section 12.2.1 for AE reporting procedures.

Adverse Reaction (AR)

All untoward and unintended responses to an IMP related to any dose administered. A causal relationship between an IMP and an adverse event is at least a reasonable possibility, i.e. the relationship cannot be ruled out.

Serious Adverse Event (SAE) or Serious Adverse Reaction (SAR)

An adverse event or adverse reaction that at any dose:

- Results in death
- Is life threatening (the term “life-threatening” refers to an event in which the patient was at risk of death at the time of the event. It does not refer to an event that hypothetically might have caused death if it were more severe)
- Requires in-patient hospitalisation or prolongs existing hospitalisation
- Results in persistent or significant disability/incapacity
- Is a congenital anomaly or birth defect
- Is otherwise medically significant (e.g. important medical events that may not be immediately life-threatening or result in death or hospitalisation but may jeopardise the patient or may require intervention to prevent one of the other outcomes listed above)

See section 12.2.2 for SAE reporting procedures.

Suspected Unexpected Serious Adverse Reaction (SUSAR)

A serious adverse reaction, the nature or severity of which is not consistent with the applicable reference safety information.

i.e. an adverse event that meets all the following criteria:

- Serious – meets one or more of the serious criteria, listed under the definition of SAE above
- Related – assessed by the local PI or designee, or Sponsor as causally related to one or more elements of the trial treatment

- Unexpected – the event is not consistent with the applicable reference safety information

See section 12.3 for reporting procedures for these events.

Adverse event of special interest (AESI)

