12.2. Reporting Procedures

Adverse Event Term

An adverse event term must be provided for each adverse event. Wherever possible a valid term listed in the Common Terminology Criteria for Adverse Events (CTCAE) v5.0 should be used. This is available online at:

https://ctep.cancer.gov/protocoldevelopment/electronic_applications/docs/CTCAE_v5_Quick_Reference_8.5x11.pdf

Severity grade of each adverse event must be determined by using CTCAE v5.

Causality

The relationship between the treatment and an adverse event will be assessed.

For AEs (including SAEs), the local PI or designee will assess whether the event is causally related to each IMP.

For SAEs, a review will also be carried out by the Sponsor's delegate.

Causal relationship to each trial treatment must be determined as follows:

- Related (reasonable possibility) to an IMP
- Not related (no reasonable possibility) to an IMP

UCL CTC will consider events evaluated as related to be adverse reactions.

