12.2.1. Reporting of Adverse Events (AEs)

All adverse events that occur between informed consent and 5 months post last IMP administration must be recorded in the patient medical notes and the trial CRFs.

An AE cover sheet should be completed and a photocopy submitted to UCL CTC at each trial visit. The Adverse Event form should be submitted when there are new AEs or changes to existing AEs on the form. Any updates or changes to previously reported AEs must be initialed and dated. Report the worst grade observed for the AE on the form.

Those meeting the definition of a Serious Adverse Event (SAE) or Adverse Event of Special Interest (AESI) must also be reported to UCL CTC using the trial specific SAE Report. Also refer to section 12.2.2 (Reporting of Serious Adverse Events (SAEs)) and section 12.4 (Adverse Events of Special Interest)). Adverse events meeting the definition of an Urgent Event must be reported on an Urgent Event form (see section 12.5 Urgent Events).

Pre-existing conditions (i.e. conditions present at registration) do not qualify as adverse events unless they worsen or recur (i.e. improves/resolves and then worsens/reappears again).

E.g. an AE could be an exacerbation of a chronic or intermittent pre-existing condition including either an increase in frequency and/or intensity of the condition (worsening of the event). Another example of an AE is when a pre-existing condition improves during the trial (e.g. from grade 3 to grade 1) and then it worsens again (e.g. from grade 1 to grade 2), even if the event is of severity equal or lower to the original condition (improvement and recurrence of the event).

NB the disease(s) under study and its anticipated day-to-day fluctuations would not be an AE.

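### Section 17.2.2: adverse event presentation 3 stops at grade 4 while the other three use 3+, so fatal events drop out of its severe band

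*Combined protocol and SAP*

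**What the plan says.** In section 17.2.2, under safety and tolerability, the plan sets out four ways of presenting adverse event rates:

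- Presentation 1, worst grade over the whole trial: "the number of patients who experience a grade 1-2 or 3+ event at any time point".
- Presentation 2, worst grade within each cycle: "the number of patients who experience a grade 1-2 or 3+ event during each cycle".
- Presentation 3, share of cycles: "Proportion of cycles where patients experience a grade 1-2 or grade 3-4 AE".
- Presentation 4, count per cycle: "Median number of grade 1-2 or 3+ AEs (of any type) experienced at each cycle".

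Three other places matter. Section 12.2 fixes the scale: "Severity grade of each adverse event must be determined by using CTCAE v5". Section 12.1 makes death a seriousness criterion for an adverse event: "Results in death". Section 12.2.1 tells sites what to record when an event changes grade: "Report the worst grade observed for the AE on the form".

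**The concern.** Three of the four presentations have an open-ended severe band that includes grade 5. The remaining one closes the band at grade 4. No sentence says that grade 5 is left out on purpose, that fatal events are added back, or that they are shown next to the table.

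The omission runs in one direction only, because the grade left out is the most severe. A reader who compares presentation 3 with presentations 2 and 4 would be comparing different definitions of severe without being told. Safety and tolerability is the first secondary endpoint listed in section 3.2.2, and section 17.2.2 names burden over time as a specific aim of the safety analysis, so the per-cycle tables should agree with one another.

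**Working it through.** The plan states no figure that depends on this wording. The check is therefore a comparison of texts, followed by an illustration of size.

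**Step 1. Is grade 5 a live category here?** Yes. Events are graded by CTCAE v5 (section 12.2), fatal events are adverse events (section 12.1), and section 2.1.6 describes an earlier pembrolizumab study with the band "grade 3-5 drug-related AEs". Section 17.3 foresees treatment-related deaths by setting a trigger for IDMC review.

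**Step 2. Would a fatal event also be captured as grade 3 or 4?** Not for the same event. Section 12.2.1 asks for the worst grade, so an event that worsens to death is held as grade 5.

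**Step 3. Classify example cycles under each wording of the severe band.**

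| Events in the cycle | Severe under 3-4? | Severe under 3+? |
|---|---|---|
| Grade 5 only | No (in neither band) | Yes |
| Grade 5 and a grade 2 | No (in grade 1-2 only) | Yes |
| Grade 5 and a separate grade 3 | Yes | Yes |
| Grade 3 only | Yes | Yes |

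The fatal event itself is always left out of presentation 3. The classification of the cycle changes only in the first two rows, where no separate grade 3 or 4 event occurred in the same cycle.

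**Step 4. Size.** Inputs: 42 patients (section 17.1) and at most 18 cycles each (section 8.2). The mean of 6 cycles is my assumption, to show the effect of early stopping. I also assume that the proportion is pooled over all patients' cycles and that each death affects one cycle.

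Shift in percentage points = 100 × d / C, where d is the number of deaths of the kind in the first two rows and C is the total number of cycles.

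- C = 42 × 18 = 756: one death gives 100 × 1/756 = 0.13; five give 100 × 5/756 = 0.66.
- C = 42 × 6 = 252: one death gives 100 × 1/252 = 0.40; five give 100 × 5/252 = 1.98.

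Five is used because 10% of 42 is 4.2, so five is the first count above the 10% level in section 17.3. It is an illustration, not a forecast. The 756-cycle total is a ceiling that could not be reached if patients died on treatment, so for a death of this kind 0.13 is the low end of the shift. A death with a separate grade 3 or 4 event in the same cycle shifts nothing. The same holds for a fatal event outside any treatment cycle, which is possible because events are collected until 5 months after the last dose.

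**The case against.** The best reply is that nothing is hidden. Presentation 2 is also by cycle and uses 3+, so a fatal event in a given cycle appears there. Presentations 1 and 4 include it as well. Deaths from any cause go on a dedicated form (section 12.5), enter progression-free and overall survival, and are counted directly for the IDMC trigger if treatment related. Section 17.2.2 states that all adverse event analysis is descriptive. A table labelled grade 3-4 is also literally correct for what it counts. All of this stands, and it limits the point to one table that does not match its neighbours.

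A second reply is that death ends treatment and is not a recurring burden, so leaving it out of a burden measure could be deliberate. That is possible, but the plan does not say so, and presentation 4, which also describes burden by cycle, keeps 3+. The option to restrict presentations 3 and 4 to clinical events does not explain the difference either: it concerns lower-level laboratory events and applies equally to both.

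A reader might infer three stronger things that the documents do not support:

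- That every cycle with a fatal event would look free of severe toxicity. This fails whenever a separate grade 3 or 4 event occurred in that cycle.
- That presentation 3 is the plan's principal measure of burden. The four presentations are not ranked, and two others are also by cycle.
- That the plan conceals deaths. They are reported in several other places.

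**Conclusion.** The inconsistency is real and minor. As written, presentation 3 leaves grade 5 events out of its severe band, and a cycle whose only severe event is fatal is not counted as a cycle with a severe event. The shift is about 0.13 percentage points per such death at the 756-cycle maximum and about 0.40 points at an assumed mean of 6 cycles, under the pooling and one-cycle-per-death assumptions stated above. The primary endpoint, the sample size and the IDMC trigger do not depend on it. It may be no more than a slip of wording, but it is an analysis instruction that a programmer could follow literally, so it is worth correcting.

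**What to change.** In section 17.2.2, presentation 3, replace grade 3-4 with grade 3+, so that all four presentations share one severe band. If the exclusion of grade 5 is intended, say so in the plan and in the table, and show grade 5 events by cycle beside it. Either is a short text edit that needs no new data, no additional patients and no change to the other analyses.
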